## SECTION V: RESEARCH PLAN

1. **Statement of Purpose:** State the scientific aim(s) of the study, or the hypotheses to be tested.

The specific aims with respect to increasing uptake of effective counseling and medications for tobacco, alcohol and opioid use disorders (addiction treatments) in four HIV clinics are:

**Aim 1.** Among key stakeholders, to use quantitative and qualitative (mixed) methods to identify the site-specific evidence, context and facilitation-related barriers and facilitators to the integration of addiction treatments to help tailor an Implementation Facilitation for each clinic.

**Aim 2.** To evaluate the impact of Implementation Facilitation on:

2a: Organizational readiness to deliver addiction treatments

2b: Provider readiness to deliver addiction treatments

2c: Provision of addiction treatments

2d: Changes in organizational models of care used to deliver addiction treatments

**Aim 3.** To evaluate the impact of Implementation Facilitation on ART receipt, viral suppression, VACS Index, and retention in HIV care among patients eligible for addiction treatment.

2. **Background:** Describe the background information that led to the plan for this project. Provide references to support the expectation of obtaining useful scientific data.

**Why focus on tobacco, alcohol and opioid use disorders?** These disorders are prevalent in HIV clinics, often co-occur, and effective counseling and medication treatments exist.

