## **Implementation Facilitation leads to practice change**

Defined as a “process of ‘helping individuals and teams to understand what they need to change and how they need to change it in order to apply evidence to practice,’” Implementation Facilitation is an effective intervention that includes a “deliberate process of interactive problem solving and support that occurs in the context of a recognized need for improvement and supportive interpersonal relationship.” (Table 2)

**Research Plan:** Summarize the study design and research procedures using non-technical language that can be readily understood by someone outside the discipline. **Be sure to distinguish between standard of care vs. research procedures when applicable, and include any flowcharts of visits specifying their individual times and lengths.** Describe the setting in which the research will take place.

The **Working with HIV clinics to adopt Addiction Treatments using Implementation Facilitation (WHAT IF?)** study will evaluate the impact of Implementation Facilitation on the adoption of addiction treatment services in four HIV clinics. We will use a stepped wedge design (See Table 4). The stepped wedge design is a variation on a cluster randomized clinical trial in which participating sites are randomly assigned a time at which the intervention (Implementation Facilitation) is begun. The primary comparison is of the change that occurs from the pre-implementation period to two post-implementation periods, the initial six months (evaluation) and the following six months (maintenance). This proposal will consist of three main components in each of four clinics: 1) **formative evaluation** with key stakeholders at each site to guide and refine the Implementation Facilitation, 2) **conduct of the Implementation Facilitation** and 3) an **evaluation of the impact** of the Implementation Facilitation on organization and provider-level readiness, provision of addiction treatments, and HIV outcomes.

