**Analysis for Aim 2a, 2b, and 2c:** Number (percent) will be used to present data from categorical variables. Continuous variable data will be presented as means (+/- SD) and those with a non-normal distribution will be characterized using medians (interquartile range). Differences across the clinics will be assessed using appropriate parametric or non-parametric techniques. The provision of addiction treatments among those eligible (Aim 2c) will be expressed as a percentage and the distribution of results in the control (unexposed) periods will be compared with those in the evaluation (exposed) and maintenance (exposed) periods. Characteristics of patients and clinics will be shown by randomization status in each step of the design. We will conduct similar analyses for the measures of organizational and provider readiness (Aims 2a, 2b) where the dependent variable will be expressed as continuous measures (ORCA score and change rulers). Based on the PARIHS, we hypothesize that stakeholder scores on the ORCA subscales including clinical experiences, patient preferences, leadership culture

and measurement will mediate the proportion of patients receiving addiction treatment. We will test the relationship among this outcome and these mediators. To test the significance of the mediation effect, which is called the indirect effect, we will calculate Sobel's test for each proposed mediator. We will use an intent-to-treat approach (i.e. cluster analysis will be done) according to the time clinics were intended to cross over from control to Implementation Facilitation. A linear mixed model will be used, adjusting for calendar time (a potential confounder due to its association with both exposure to the intervention and outcome), with a random effect for clinic, a fixed effect for each step and allowing for repeated measures for patients in the clinics. Since the population of the clinics participating in the proposed trial will be rather stable, thus rendering this a cohort stepped wedge design, an additional random effect for patients in each clinic will be introduced.

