**Analysis for Aim 2d:** To determine the impact of Implementation Facilitation on models of care we will describe the extent to which the provision of treatment for each substance is coordinated (facilitated by the HIV clinic), co-located (provided in the clinic) or integrated (provided by the primary HIV provider) by clinic. We will track changes in these models of care from the control period to the evaluation and maintenance periods.

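### Aim 2d promises the impact of Implementation Facilitation on models of care but plans only a within-clinic change from control to later periods, with no allowance for calendar time

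*Combined protocol and SAP*

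**What the plan says.** Section V, Statement of Purpose, lists "2d: Changes in organizational models of care used to deliver addiction treatments" among the things on which the impact of Implementation Facilitation will be evaluated. The Research Plan describes a stepped wedge in which "participating sites are randomly assigned a time at which the intervention (Implementation Facilitation) is begun".

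Under Statistical Considerations, the paragraph headed "Analysis for Aim 2a, 2b, and 2c" specifies a linear mixed model. On time, its wording is "adjusting for calendar time (a potential confounder due to its association with both exposure to the intervention and outcome". The remaining structure of the model is stated separately: "with a random effect for clinic, a fixed effect for each step and allowing for repeated measures for patients in the clinics".

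Aim 2d has its own paragraph. It opens with a causal purpose and a descriptive method: "To determine the impact of Implementation Facilitation on models of care we will describe the extent to which the provision of treatment for each substance". The categories to be described, clinic by clinic, are coordinated, co-located and integrated care. The paragraph ends: "We will track changes in these models of care from the control period to the evaluation and maintenance periods". It names no model, time term, test or comparator clinic, and no other section extends the Aim 2a to 2c adjustment to Aim 2d.

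**The concern.** What is randomised is when each clinic crosses over. The comparison that randomisation protects is therefore between clinics that have crossed over and clinics that have not, in the same calendar period. A change within one clinic from its control periods to its later periods does not use that comparison. It mixes any effect of facilitation with whatever else changed over the same months.

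The plan accepts this reasoning for Aims 2a to 2c and adjusts for calendar time there. Aim 2d runs on the same schedule without that protection. Table 4 has seven columns, or 3.5 years at six months each, and Table 5 schedules COVID-19 data at the maintenance assessment only. A change in how clinics deliver addiction care that has nothing to do with facilitation is therefore a realistic possibility. Followed as written, the plan would report such a change as part of the impact of Implementation Facilitation on models of care.

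**Working it through.** **Plan's own figure.** Aim 2d has none. The only stated calculation is the Aim 2c sample size. The quoted design effect reproduces: [1 + 0.01(1200 + 300 − 1)] / [1 + 0.01(600 + 300 − 1)] × 3(0.99) / [2(4 − 1/4)] = 0.634, and 592 × 0.634 ≈ 375. It plays no part below.

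**Inputs.** The schedule is Table 4: four clinics, seven columns. Each column is taken as six months, from the phase length in the Aim 2 and 3 overview. The size of any shared trend is not in the documents, so 1, 2 and 3 percentage points per period are assumed, with a true effect of zero.

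**Step 1: distance in time between the phases compared.**

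| Clinic | Control columns (mean) | Evaluation column | Gap | Maintenance columns (mean) | Gap |
|---|---|---|---|---|---|
| 1 | 1–4 (2.5) | 6 | 3.5 | 7 (7.0) | 4.5 |
| 2 | 1–3 (2.0) | 5 | 3.0 | 6–7 (6.5) | 4.5 |
| 3 | 1–2 (1.5) | 4 | 2.5 | 5–7 (6.0) | 4.5 |
| 4 | 1 (1.0) | 3 | 2.0 | 4–7 (5.5) | 4.5 |

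The average gap is (3.5 + 3.0 + 2.5 + 2.0)/4 = 2.75 periods for evaluation (2.75 × 6 = 16.5 months) and 4.5 periods for maintenance (27 months). If only the last control column, the evaluation column and the first maintenance column are used, the gaps are 2 and 3 periods in every clinic. In every clinic, all evaluation and maintenance cells fall after all control cells.

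**Step 2: apparent change with no true effect.** For a linear shared trend, apparent change = trend per period × gap.

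| Assumed trend (points per period) | Evaluation, all columns | Maintenance, all columns | Evaluation, adjacent windows | Maintenance, adjacent windows |
|---|---|---|---|---|
| 1 | 2.75 | 4.5 | 2 | 3 |
| 2 | 5.5 | 9.0 | 4 | 6 |
| 3 | 8.25 | 13.5 | 6 | 9 |

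**Step 3: what the design offers instead.** In column 3, clinic 4 is in evaluation while clinics 1 and 2 are in control. In column 4, clinic 3 is in evaluation and clinic 4 in maintenance while clinic 1 is in control. From column 5 on, no clinic is in control.

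**Step 4: whether period terms would remove the trend.** Using all 28 cells, a model with clinic, phase and period terms has full rank (13 of 13). It returns zero for the evaluation and maintenance effects at each assumed trend. With only three adjacent windows per clinic, linear time equals the clinic's last control column + 2 × evaluation + 3 × maintenance. The design matrix then has rank 11 of 12, and the two effects cannot be separated from a trend.

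**Step 5: precision of an adjusted estimate.** Assume 24 treated patients per clinic-column (94 × 26% ≈ 24), a 30% share with integrated care and an intracluster correlation of 0.01, and leave out the facilitation cells. The step-adjusted standard error is then about 9 to 10 points for evaluation and 11 to 13 for maintenance, depending on whether clinic is random or fixed. The 95% limits are roughly ±18 to ±20 and ±22 to ±25 points, before any split by substance.

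**The case against.** The strongest reply is that Aim 2d is descriptive. It describes and tracks, by clinic and by substance, and defines no pooled contrast, interval or test. On that view there is no estimator to be biased, and nothing stops the investigators from setting the description against the staggered schedule. This would settle the matter if the paragraph claimed only description, but it opens with "To determine the impact of Implementation Facilitation on models of care we will describe the extent". While that purpose stands, a reader will take the tracked change as the effect.

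Other parts of the reply do stand:

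- The plan elsewhere speaks of three six-month phases and of baseline, 6-month and 12-month assessments, so adjacent windows may be what is meant. The smaller figures (4 and 6 points at the 2-point trend) would then apply.
- A reader might express the problem as an inflated false-positive rate. Aim 2d names no test, so the documents support no such rate; only the size in points can be given.
- A reader might conclude that the Aim 2c mixed model must be imposed on Aim 2d. The documents do not support that as a requirement. Table 5 lists no models-of-care item, no section names a data source for the classification, and Step 5 shows how imprecise the estimate would be.
- A reader might infer that the trial has no concurrent controls. It has them in columns 3 and 4; the Aim 2d text simply does not use them.

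**Conclusion.** The point holds as a mismatch between claim and analysis. As written, Aim 2d would credit any trend shared by the clinics to Implementation Facilitation. The shared trend enters multiplied by an average of 2.75 periods for evaluation and 4.5 for maintenance, or by 2 and 3 with adjacent windows. At an assumed 2 points per period that is about 5.5 and 9 points, or 4 and 6. The multipliers come from Table 4. The trend, its linearity and its being common to all clinics are assumptions.

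A reader might go further and think the trial's main result is affected. It is not: the primary outcome is provision of treatment under Aim 2c, and its model includes calendar time, step and clinic. The consequence is confined to what may be concluded about models of care.

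**What to change.** In the Aim 2d paragraph:

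1. Report coordinated, co-located and integrated provision by clinic, substance and Table 4 column. Show crossed-over clinics beside clinics still in control in the same column (columns 3 and 4), and state that none remain from column 5.
2. Label the change from control to evaluation and maintenance as uncontrolled description that is not attributed to Implementation Facilitation, and reword the opening purpose to match.
3. Name the data source and the rule for classifying the model of care.

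A step-adjusted estimate along the lines of Aim 2c is optional. It requires classification in every column, because three adjacent windows per clinic cannot support it, and it should be presented as imprecise.

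The cost is classifying care by column instead of by three phases, and a weaker claim for Aim 2d. The work involved cannot be judged from the documents, since they do not say where the classification comes from. The Aim 2c analysis and its sample size do not change.

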### **Evaluating the Effectiveness of the Implementation Facilitation (Aim 2 and Aim 3)**

#### Overview

We will use a stepped wedge design (Table 4) to evaluate the effect of the Implementation Facilitation on the outcomes. In a stepped wedge design, clinics are randomly assigned to time cohorts and then followed prospectively to determine their outcome status. Stepped wedge designs are increasingly used to promote the implementation of evidence-based practice and are appropriate for evaluating interventions where there is evidence that the intervention is likely to be beneficial and when practical considerations require sequential deployment of an intervention. We will have three phases of six-months each: 1) a pre-implementation control period, 2) a post-intervention evaluation period, and 3) a maintenance period. The proportion of eligible patients in each time period who receive at least one addiction treatment will be assessed and the effect of the intervention will be evaluated by comparing pre-implementation to evaluation and maintenance periods. This will allow us to assess the short and long-term (maintenance) impact of Implementation Facilitation.

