**Analysis for Aim 3:** These analyses will be restricted to patients diagnosed with a tobacco, alcohol or opioid use disorder. ART receipt will be defined as at least 180 days of three concurrent antiretroviral agents in the 6-month interval based on prescriptions in the electronic medical record. Viral suppression, will be defined as HIV RNA <200 copies/mL at last test closest to the time of data extraction, consistent with Department of Health and Human Services (DHHS) guidelines. Although current limits of detection are lower, this cutoff allows for low-level “blips” that have no clinical significance. The VACS Index will be evaluated based on most recent values at the time of data extraction. VACS Index score will be treated as a continuous variable. Retention in HIV care, per DHHS guidelines uses a 24-month measurement period. It is defined as at least one HIV medical care visit in each 6-month period, with a minimum of 60 days between the first medical visit in the prior 6-month period and the last medical visit in the subsequent 6-month period. This measure has good agreement with the Institute of Medicine indicator for retention in care and is an independent predictor of mortality. We will evaluate whether patients have had at least 1 visit in the 6-month period prior to time of data extraction. These analyses will be adjusted for demographics (age, gender), and presence of psychiatric diagnosis (anxiety, major depression, severe mental illness). We will use descriptive statistics to characterize addiction treatment eligible patients overall and by substance at baseline and examine changes at each interval. We will then examine each of these HIV-related outcomes at the 6-month intervals of control, evaluation and maintenance phases based on the provision of addiction treatment. We will determine the association between provision of addiction treatment, including benzodiazepines and outcomes with the MIXED models procedure repeated measures and generalized estimating equations (GEE) to account for repeated measures for dichotomous outcomes. We will adjust for fixed demographics, substance use disorder and psychiatric diagnoses. We will describe the association with odds ratios and 95% confidence intervals. For continuous outcomes, we will use multivariable linear regression with GEE with similar adjustment.

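### Aim 3 asks for the effect of Implementation Facilitation on HIV outcomes, but its analysis models only the association with addiction treatment received, and its power claim is borrowed from another outcome

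*Combined protocol and SAP*

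**What the plan says.** Section V.1 (Statement of Purpose) gives Aim 3 as: "To evaluate the impact of Implementation Facilitation on ART receipt, viral suppression, VACS Index, and retention in HIV care". The Research Plan says "The primary comparison is of the change that occurs from the pre-implementation period to two post-implementation periods", and it lists the impact "of the Implementation Facilitation on organization and provider-level readiness, provision of addiction treatments, and HIV outcomes" as a component of the study. The Overview under the heading for evaluating effectiveness (Aims 2 and 3) adds: "We will use a stepped wedge design (Table 4) to evaluate the effect of the Implementation Facilitation on the outcomes".

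Section V.11, Analysis for Aim 3, proceeds differently. After a descriptive step, it looks at the HIV outcomes in the "control, evaluation and maintenance phases based on the provision of addiction treatment". Its inferential sentence reads "We will determine the association between provision of addiction treatment, including benzodiazepines and outcomes", using mixed models and GEE, with odds ratios for dichotomous outcomes. On covariates it says: "We will adjust for fixed demographics, substance use disorder and psychiatric diagnoses".

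The model with a clinic random effect, step effects and intent-to-treat by planned crossover time is in the preceding section, headed Aims 2a, 2b and 2c. That section describes its model as "adjusting for calendar time (a potential confounder due to its association with both exposure to the intervention and outcome".

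The section on adequacy of sample size works only with the proportion receiving addiction treatment (15% to 26% to 33%). It then declares the quantitative analyses of Aims 2 and 3 adequately powered as well.

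**The concern.** What is randomised is each clinic's start time. Whether an individual patient receives addiction treatment is not randomised: it is decided after baseline by patient and provider. The Aim 3 model, with its patient-level covariates and repeated measures, is most naturally read as using each patient's own receipt as the exposure. Its coefficient compares treated with untreated patients. It does not estimate what Facilitation does to the HIV outcomes of a clinic's eligible population, which is what the aim names.

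Two things are at stake. A treated-versus-untreated association could stand in the report where the Facilitation effect belongs. And a null Aim 3 result could be read as coming from an adequately powered comparison when nothing in the plan supports that.

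A smaller wording point: benzodiazepines are written as part of addiction treatment in the Aim 3 model, yet they are not among the Table 3 medications, and Table 5 collects them only at 12 months.

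**Working it through.** **1. The plan's own figure.** Inputs from the sample size section: 15% vs 26%, alpha 0.05, power 90%, n = 300 per clinic, ICC 0.01, k = 4, b = 1, t = 1.
- Two proportions, two-sided, continuity-corrected: 299 per arm, 598 in total, against the stated 592 (close).
- Design effect = [1 + ρ(ktn + bn − 1)] / [1 + ρ(ktn/2 + bn − 1)] × 3(1 − ρ) / [2t(k − 1/k)] = (15.99/9.99) × 0.396 = 0.634. Then 592 × 0.634 = 375, or 94 per clinic.

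The stated 0.63 and 375 reproduce. Every input concerns provision. No HIV-outcome baseline, SD, effect size or ICC enters.

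**2. The two quantities.** Let B be the benefit per treated patient on the risk-difference scale, or in VACS Index units. If Facilitation acts only through provision:
- evaluation: (0.26 − 0.15)B = 0.11B; ratio 1/0.11 = 9.1
- maintenance: (0.33 − 0.15)B = 0.18B; ratio 1/0.18 = 5.6 (the text says 19 points; 33 − 15 is 18)

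On the log-odds scale the ratio depends on baseline. With an assumed average of 75%, 15% already treated and B = 20 points, untreated patients are at 72% and treated at 92%, so the log odds ratio is ln(11.5/2.571) = 1.498. The Facilitation contrast, 77.2% vs 75%, gives ln(3.386/3) = 0.121. The ratio is about 12.

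**3. The omitted time and clinic terms.** Table 4 has 24 cells outside the IF step: 10 control, 4 evaluation, 10 maintenance. Their period numbers sum to 20, 18 and 60.
- Mean period, treated: (0.15×20 + 0.26×18 + 0.33×60)/5.84 = 4.71
- Mean period, untreated: (0.85×20 + 0.74×18 + 0.67×60)/18.16 = 3.88
- Gap: 0.82 periods, or 0.41 years. An assumed trend of 1–3 points per year adds 0.4–1.2 points; an assumed 10-point gradient across clinics adds 0.7.
- With one window per phase (12 cells) the gap is 0.50 periods (0.25–0.74 points) and the clinic part is zero.

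This is the smaller part. Bias from self-selection into treatment cannot be derived from the documents.

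**4. Power for the Facilitation effect (illustration only).** Assumed: binary outcome with baseline 75–85%, ICC 0.01 carried over from provision, within-patient correlation 0–0.7, closed cohort, normal approximation, two-sided 0.05, no small-sample correction. Model: fixed period effects, separate evaluation and maintenance effects, random clinic effect, fitted by generalised least squares. Power ≈ Φ(δ/SE − 1.96). With B = 20 points, δ is 0.11 × 20 = 2.2 (evaluation) and 0.18 × 20 = 3.6 (maintenance).

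| Cells, patients per clinic-period | SE, evaluation (points) | Power, evaluation | Power, maintenance |
|---|---|---|---|
| 24 cells, 300 | 1.16–2.54 | 14–48% | 19–65% |
| 24 cells, 94 | – | 8–19% | 10–26% |
| 24 cells, 575 | – | 22–75% | 32–90% |
| 12 cells (three windows), 300 | – | 8–9% | 8–11% |

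At 300 with 24 cells, B = 10 gives 7–16% and 8–22%; B = 25 gives 19–66% and 27–84%. The difference detectable with 90% power is 3.24 × SE: 3.8–8.2 points (evaluation) and 5.0–10.8 (maintenance). Divided by 0.11 and 0.18, these need B of 34–75 and 28–60 points. For VACS Index the detectable differences are 0.105–0.190 SD and 0.139–0.250 SD.

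A simple check without the mixed model: a parallel-group comparison with 90% power at baseline 75–85% needs 5,192–7,892 per arm for 2.2 points, against the plan's 296.

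**5. Three windows per clinic.** The sample size section speaks of three primary time points, and Table 5 has three columns. With one control, one evaluation and one maintenance window per clinic, evaluation always falls two periods after the last control window and maintenance three. So 2 × evaluation + 3 × maintenance equals period minus a clinic constant. With clinic as a fixed effect the design has rank 11 for 12 parameters, and the two phase effects cannot be separated. With a random clinic effect they rest on between-clinic differences.

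**The case against.** The best defence is that the intended comparison is stated. The Overview's heading covers Aim 3, the Research Plan counts HIV outcomes among the impacts, and the missing-data section applies intent-to-treat to all randomised clinics. The Aim 3 section itself mentions changes at each interval, and it calls the provision result an association. That association is a legitimate question in a hybrid implementation study. On this reading a model is unspecified, but the aim is not abandoned. The intention is indeed clear. It is not carried into any Aim 3 model, however: the interval sentence is descriptive, and the model that is specified answers the other question.

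The second defence concerns size. The 9.1 and 5.6 are arithmetic on the plan's provision rates, assume action only through provision, and do not carry over to odds ratios. That is right, but the odds-scale example in the working shows a gap at least as large.

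The power figures rest on assumed inputs. A 20-point benefit at an 85% baseline exceeds the 15 points of headroom unless treated patients start below average. The 94 is a required minimum. Table 3's untreated counts sum to 355–765 per listed clinic (mean 575, less any co-occurrence), which would raise all-cell power to 22–75% and 32–90%. These points stand, so the figures illustrate and do not prove low power. In the other direction, the three-window reading has better textual support than the 24-cell one and gives much lower power.

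**Conclusion.** The concern holds: the Aim 3 analysis is wrong as written for the aim it serves. The absence of a Facilitation term, and of any Aim 3 input behind the power statement, follows from the text without assumptions. The 9.1- and 5.6-fold differences rest on the plan's 15/26/33% and on action through provision alone. The power ranges are illustrative and depend on assumed baselines, correlations and benefit. The omitted time and clinic terms matter less, at roughly 0.25–1.2 points for trend and up to 0.7 for clinic under the assumed gradients. HIV outcomes are secondary and the primary provision analysis is unaffected, so this should be fixed but does not threaten the trial's main result.

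**What to change.** - Make the main Aim 3 analysis an intent-to-treat comparison of control with evaluation, and of control with maintenance, by randomised crossover time. Extend the Aim 2a–2c structure: fixed period effects, random clinic effect, random patient effect, plus the covariates already listed for Aim 3. Use a logistic link for antiretroviral receipt, suppression and retention, and a linear model for VACS Index.
- State the reporting scale, which Table 4 periods enter, and a small-sample method suited to four clinics. A permutation test over the 4! = 24 clinic orders cannot give a p-value below 1/24 = 0.042.
- Keep the provision association, labelled exploratory and non-randomised. Model benzodiazepines separately from addiction treatment.
- Remove Aim 3 from the power sentence, or replace it with detectable differences for both phases under stated assumptions.

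The cost is SAP wording and one extra model per outcome on record data already planned. Further record windows are needed only if no more than three per clinic are extracted. The price is wider intervals and openly low power for Aim 3.
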